8.2 Recording of Adverse Events

The study will collect all Grade 3 and above adverse events (*except* abnormal labs as outlined in section 8.1, and the exceptions listed below), regardless of relationship to study therapy or study procedures. Severity grading will be based on the current version of the Common Terminology Criteria for Adverse Events (CTCAE). Grade 1 and 2 events will not be collected.

Adverse events will be collected from the time the patient signs the informed consent until 30 days after the last dose of Ixazomib. Events that occur after this time will be recorded only if there is a reasonable possibility that the event was caused by a study procedure or Ixazomib. All recordable adverse events will be followed until resolution.

Reporting procedures:

- All non-serious, Grade 3 and above adverse events must be recorded in the database within 20 days of becoming aware of the event.
- Exceptions:

The following are frequent events in the chronic GVHD population and will not be recorded as adverse events *as long as they are not serious*:

- Abnormalities present at study enrollment: Will not be considered adverse events, unless such abnormalities worsen (i.e. increase in frequency, intensity, or present new complications or untoward events) during study follow up
- Electrolyte abnormalities: Increase or decrease in sodium, potassium, chloride, bicarbonate, phosphorus, magnesium, calcium, hyperglycemia following steroid

therapy

- **Ocular:** GVHD related eye dryness, discomfort, requirement for moisturizing eye drops or other topical GVHD ocular therapies or interventions (e.g. punctal plugs, scleral lenses), changes in visual acuity.
- **Dermatology:** Nail changes, GVHD rash (to include erythema, scleroderma, ulceration, lichenoid changes, hyper- or hypo-pigmentation, dry skin and alopecia) or cushingoid appearance due to steroid therapy.
- **Gastrointestinal:** Xerostomia, oral ulcers or other GVHD associated lesions, oral pain or sensitivity, anorexia, difficulty swallowing due to esophageal stricture or narrowing, nausea/vomiting, salivary gland changes, GVHD associated abdominal pain, bloating, diarrhea, weight loss
- **Respiratory:** shortness of breath, cough, or oxygen requirement associated with pulmonary chronic GVHD involvement
- **Growth and Development:** Reduced growth velocity, delayed puberty.

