- **Musculoskeletal changes:** Avascular necrosis, fracture, arthritis, osteoporosis, decrease in range of motion associated with joint or fascial GVHD involvement
- **Sexual Function:** Erectile dysfunction, infertility, amenorrhea, vaginal stenosis, vaginal dryness or discomfort.
- **Events secondary to routine procedures performed for chronic GVHD therapies:** Extracorporeal photopheresis, PUVA therapy.

Non-serious adverse events collected in the database will be compiled by the coordinating center and reported to the DSMB approximately every 6 months.

All **serious adverse events** must be reported in the database within 24 hours of becoming aware of the event. Significant and relevant follow-up information should also be reported as soon as possible.

- **Exception:**
 - Hospitalization for elective treatment of a pre-existing condition that did not worsen from baseline is not considered an SAE.

The database will notify the coordinating center and sponsor-investigator when a serious adverse event has been entered. The sponsor-investigator will then determine whether the event meets the criteria for expedited reporting (see below) and will work with the coordinating center to prepare the IND Safety Report.

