8.4 Reporting to Millennium

AEs which are serious must be reported to Millennium Pharmacovigilance (or designee) from the date the participant signs Informed Consent through 30 days after administration of the last dose of Ixazomib. Any SAE that occurs at any time after completion of Ixazomib treatment or after the designated follow-up period that the sponsor-investigator and/or sub-

investigator considers to be related to any study drug must be reported to Millennium Pharmacovigilance (or designee). In addition, new primary malignancies that occur during the follow-up period must be reported, regardless of causality to study regimen.

Additionally, if the investigator learns of a new primary malignancy occurring in a study participant within 3 years after the last dose of study drug, it must be reported to Millennium Pharmacovigilance.

Planned hospital admissions or surgical procedures for an illness or disease that existed before the patient was enrolled in the trial are not to be considered AEs unless the condition deteriorated in an unexpected manner during the trial (e.g., surgery was performed earlier or later than planned). All SAEs should be monitored until they are resolved or are clearly determined to be due to a patient's stable or chronic condition or intercurrent illness(es).

Since this is an investigator-initiated study, the principal investigator also referred to as the sponsor-investigator, is responsible for reporting serious adverse events (SAEs) to any regulatory agency and to the sponsor- investigator's EC or IRB.

Regardless of expectedness or causality, all SAEs (including serious pretreatment events) must also be reported to Millennium Pharmacovigilance:

Fatal and Life Threatening SAEs within 24 hours of the sponsor-investigator's observation or awareness of the event

All other serious (non-fatal/non life threatening) events within 4 calendar days of the sponsor-investigator's observation or awareness of the event

See below for contact information for the reporting of SAEs to Millennium Pharmacovigilance.

The sponsor-investigator must fax the SAE Form per the timelines above. A sample of an SAE Form will be provided.

The SAE report must include at minimum:

- **Event term(s)**
- **Serious criteria**

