 - o If hepatitis C antibody testing is positive, hepatitis C PCR should be tested in peripheral blood.
 - If PCR negative, the patient is eligible, but if positive, ineligible.

***AE/SAE are monitored from the time the patient signs the consent document through 30 days following the final dose of study therapy

****Acceptable window for study visits at 3, 6, and 9 months is +/- 14 days, and acceptable window for the 12 month study visit is +/- 1 month. Study visit due dates are calculated based on the date of baseline visit, and 1 month = 28 days.

▲For patients who have a CR/PR or stable disease at 6 months, and who elect to continue on ixazomib for an additional 6 cycles, there will be an additional study visit at 9 months. This visit will occur at 9 months regardless of when the additional cycles of ixazomib are started.

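### Sections 8.2 and 8.4 are not reconciled on new primary malignancies: a late second cancer judged unrelated can reach the manufacturer yet be missing from the trial database

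*Combined protocol and SAP*

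**What the plan says.** **Trial recording.** Section 8.2 sets the window: "Adverse events will be collected from the time the patient signs the informed consent until 30 days after the last dose of Ixazomib". For anything later it requires a possible link to ixazomib or a study procedure: "Events that occur after this time will be recorded only if there is a reasonable possibility that the event was caused by". It also sets a severity floor: "Grade 1 and 2 events will not be collected". Serious events "must be reported in the database within 24 hours of becoming aware of the event", and "The database will notify the coordinating center and sponsor-investigator when a serious adverse event has been entered". The three-asterisk footnote to the Study Calendar (11.1) repeats the time limit: "AE/SAE are monitored from the time the patient signs the consent document through 30 days following the final dose of study therapy". None of these places mentions new primary malignancies.

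**Reporting to the manufacturer.** Section 8.4 has its own general rule for serious events: consent to 30 days after the last dose, and later only if considered related. It then adds two duties for second cancers. First, "new primary malignancies that occur during the follow-up period must be reported, regardless of causality to study regimen". Second, if the investigator learns of one "within 3 years after the last dose of study drug, it must be reported to Millennium Pharmacovigilance". The second duty carries no causality condition.

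**Onward use.** Section 8.3 draws the IND Annual Report from events that the study collects and that do not qualify for expedited reporting.

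**The concern.** The general rules of 8.2 and 8.4 agree: 30 days after the last dose, and later only if related. Section 8.4 then lifts the causality test for one kind of event, the new primary malignancy, and 8.2 has no matching exception. For a second cancer diagnosed after the window and judged unrelated, 8.4 asks for a report and 8.2 does not let it into the trial database.

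What is at stake is the completeness of the trial's own safety record. After the window, the database would hold only those second cancers that someone had already judged possibly related. In an open-label single-arm trial that judgement is made case by case with knowledge of treatment. Section 8.1 names aggregate analysis as one basis for a suspected adverse reaction and notes that more than one occurrence is often needed. Section 8.3 gives the final causality decision to the sponsor-investigator. Both work less well on a record that attribution has already filtered.

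**Working it through.** The plan states no figure on this point, so there is none to reproduce. The check compares the texts and then dates the interval that 8.2 leaves uncovered.

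**1. The rules side by side**

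| | Section 8.2 and calendar footnote | Section 8.4, new primary malignancies |
|---|---|---|
| Recipient | Trial database | Manufacturer's pharmacovigilance unit |
| Period | Consent to 30 days after last dose | Follow-up period (undefined); also 3 years after last dose, if learned of |
| Causality after 30 days | Required | Not required |
| Grade | 3 and above | No floor stated |

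No sentence says that a report made under 8.4 must also be entered in the database. No other item captures the event. The calendar row on malignancy concerns relapse, and the recurrent-malignancy endpoint in 3.1 concerns the original disease.

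**2. Inputs for the dates**

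- Doses on days 1, 8 and 15 of 28-day cycles, up to 6 cycles, optionally 12 (Sections 4.3 and 6.1).
- Window of 30 days after the last dose (8.2).
- Clinical follow-up to one year (4.3). The calendar counts a month as 28 days, so 12 months is 12 × 28 = 336 days; a calendar year is 365 days. Both are shown.
- Assumptions: day 1 is the start of follow-up, there are no dosing delays, and the patient is still in follow-up.

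**3. Formulas**

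Last dose day after c full cycles = (c − 1) × 28 + 15. Window closes = last dose day + 30. Uncovered interval = 336 (or 365) − closing day.

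| Treatment received | Last dose | Window closes | To day 336 | To day 365 |
|---|---|---|---|---|
| Single dose | day 1 | day 31 | 305 | 334 |
| 2 cycles | 28 + 15 = day 43 | day 73 | 263 | 292 |
| 6 cycles | 5 × 28 + 15 = day 155 | day 185 | 151 | 180 |
| 12 cycles | 11 × 28 + 15 = day 323 | day 353 | 0 (353 is past 336) | 12 |

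Dosing delays, or a lag between consent and first dose, move the last dose later within follow-up and shorten these intervals.

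**4. The 3-year duty**

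3 × 365 − 30 = 1,065 days lie beyond the 8.2 window for every patient. This is the length of a duty that applies only if the investigator happens to learn of a case. Most of it falls after the one-year follow-up has ended, so it does not measure lost trial observation.

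**5. Expected number of missed cases**

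Not calculable. The documents give no second-cancer rate.

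**The case against.** The strongest reply is that 8.2 and 8.4 serve different recipients and that a 30-day window with a causality exception is a deliberate choice. Much of this stands.

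- **A reader might infer that the two sections give opposite instructions.** They do not. One governs the trial database and the other governs reports to the manufacturer, and a site can follow both.
- **A reader might infer that, because a database entry alerts the sponsor-investigator, the 8.4 duty receives no input once 8.2 has closed.** The text does not support that. Section 8.4 has sub-investigators report all serious events to the sponsor-investigator so that the manufacturer can be told, and the 3-year duty starts when the investigator learns of the case. But that route requires no database entry, so the gap in the trial's own data remains.
- **Follow-up period is undefined.** If it meant only the 30 days after the last dose, the first duty would match 8.2. That reading leaves the sentence little to do, because 8.4 already requires all serious events in that period regardless of causality. Even so, the 3-year duty would still outlast 8.2.
- **The 24-hour rule for serious events carries no time limit of its own.** It could be read as open-ended, but the window in 8.2 and the footnote, which names serious events expressly, limit it.
- **Follow-up may end early.** Sections 6.11 and 6.12 tie the end of active follow-up to treatment failure, including relapse or a new systemic agent. The intervals above are therefore maxima.
- **No planned estimate is affected.** Second-cancer incidence is not an objective, endpoint or analysis. Possibly related cases stay recordable at any time, and deaths from any cause count in overall survival. A reader should not infer that a planned result is biased.

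**Conclusion.** The point holds as an unreconciled gap in safety recording. As written, a new primary malignancy judged unrelated and diagnosed more than 30 days after the last dose can be reported to the manufacturer and still be missing from the trial database. It then has no stated route into the IND Annual Report. The DSMB provisions do not close the gap: 8.2 compiles the non-serious events in the database, and 7.1.2 adds deaths through 6 months (7 for patients who complete 6 months of treatment).

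The size depends on treatment length. Nearly the whole year is uncovered after a single dose, a little under half after 6 cycles (151/336 = 45%, 180/365 = 49%), and almost nothing after 12. These figures assume on-schedule dosing, continued follow-up, and that the follow-up period in 8.4 means the one-year study follow-up.

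It would go too far to say that the sections contradict each other, that manufacturer reporting fails, or that a second-cancer rate is understated by some amount. The primary endpoint, the stopping rule and the sample size are untouched. The change is worth making because it is cheap and because 8.2 filters on attribution the one event for which 8.4 expressly drops it.

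**What to change.** 1. In Section 8.2 and the three-asterisk calendar footnote, add an exception. New primary malignancies are entered in the study database regardless of causality or grade, from consent through the end of the 12-month follow-up, and whenever a site learns of one within 3 years of the last dose.
2. In Section 8.4, define the follow-up period.
3. State that these events are included in the IND Annual Report (8.3) and in the reports to the DSMB.

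The cost is one added sentence in each of 8.2 and the footnote, a definition, a line on reporting, and a few extra database entries. Sites already owe the same information to the manufacturer under 8.4. No endpoint, eligibility rule or treatment provision changes.

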6. STUDY DRUG

6.1 Study Drug Administration

Ixazomib will be administered at 4mg oral dose once weekly on days 1, 8, and 15 of a 28-day cycle. Up to 6 total cycles of therapy will be delivered on trial, and patients will be followed through 1 year of total clinical follow up for study endpoints.

Patients experiencing a CR, PR, or stable disease at 6 months will be given the option to continue on ixazomib for up to an additional 6 cycles (for a total of up to 12 cycles, or maximum 36 doses). See section 4.3 for additional details.

Sufficient study drug will be dispensed at each study visit to cover one 28 day treatment cycle. Study patients will document their compliance through medication logs.

Ixazomib Administration

All protocol-specific criteria for administration of study drug must be met and documented before drug administration. Study drug will be administered or dispensed only to eligible

patients under the supervision of the investigator or identified subinvestigator(s). Patients should be monitored for toxicity, as necessary, and doses of Ixazomib should be modified as needed to accommodate patient tolerance to treatment; this may include symptomatic treatment, dose interruptions, and adjustments of Ixazomib dose (see Section 6.2). Due to the common side effect of nausea, it is recommended (but not required) that participants take Zofran (ondansetron) 8 mg PO, 30-60 minutes prior to each dose, and 8 hours after each dose. Additional doses of Zofran may be taken as needed, up to 24 mg in a 24-hour period.

The prescribed administration of Ixazomib doses in this study is 4mg oral dose once weekly on days 1, 8, and 15 of a 28-day cycle. Patients should be instructed to swallow Ixazomib capsules whole, with water, and not to break, chew, or open the capsules. Study drug should be taken on an empty stomach. Patients should not have any food or drink (other than water) for at least 2 hours before taking drug, and for at least 1 hour after taking drug. A total of approximately 8 ounces (240 mL) of water should be taken with the capsule.

Missed doses can be taken as soon as the patient remembers if the next scheduled dose is 72 hours or more away. A double dose should not be taken to make up for a missed dose. If the patient vomits after taking a dose, the patient should not repeat the dose but should resume dosing at the time of the next scheduled dose.

Ixazomib Destruction

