6.6 Management of Clinical Events

Adverse drug reactions such as thrombocytopenia, diarrhea, fatigue, nausea, vomiting, and rash have been associated with Ixazomib treatment. Management guidelines regarding these events are outlined below. Further details of management of Ixazomib AEs are described in Section 6 of the Ixazomib IB.

Prophylaxis Against Risk of Infection

Infection prophylaxis should follow institutional standards.

Nausea and/or Vomiting

Standard anti-emetics may be used for prophylaxis and treatment of nausea or vomiting.

Diarrhea

Diarrhea should be managed according to clinical practice, including the administration of antidiarrheals. Fluid intake should be maintained to avoid dehydration.

Erythematous Rash With or Without Pruritus

Rash should be managed symptomatically according to standard medical practice, including supportive care, oral or topical steroids, and/or anti-histamines.

Thrombocytopenia

Blood counts should be monitored regularly as outlined in the protocol with additional testing obtained according to standard clinical practice. Ixazomib administration should be modified as noted as per dose modification recommendations in Table 6-2 when thrombocytopenia occurs. Therapy can be reinitiated at a reduced level upon recovery of platelet counts.

Neutropenia

Blood counts should be monitored regularly as outlined in the protocol with additional testing obtained according to standard clinical practice. Ixazomib administration should be modified when neutropenia occurs, as noted in the dose modification recommendations in Table 6-2. Therapy can be reinitiated at a reduced level upon recovery of absolute neutrophil counts. The use of growth factors (e.g. G-CSF) is permitted.

Fluid Deficits

Fluid deficits should be corrected before initiation of study drug and during treatment and as needed during therapy.

Hypotension

Blood pressure should be closely monitored while the patient is on study treatment and fluid deficit should be corrected as needed.

Posterior Reversible Encephalopathy Syndrome

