6. Is a **medically important event**. This refers to an AE that may not result in death, be immediately life threatening, or require hospitalization, but may be considered serious when, based on appropriate medical judgment, may jeopardize the patient, require medical or surgical intervention to prevent 1 of the outcomes listed above, or involves suspected transmission via a medicinal product of an infectious agent. Examples of such medical events include allergic bronchospasm requiring intensive treatment in an emergency room or at home, blood dyscrasias or convulsions that do not result in inpatient hospitalization, or the development of drug dependency or drug abuse; any organism, virus, or infectious particle (eg, prion protein transmitting Transmissible Spongiform Encephalopathy), pathogenic or nonpathogenic, is considered an infectious agent.

Clarification should be made between a serious AE (SAE) and an AE that is considered severe in intensity (Grade 3 or 4), because the terms serious and severe are NOT

synonymous. The general term *severe* is often used to describe the intensity (severity) of a specific event; the event itself, however, may be of relatively minor medical significance (such as a Grade 3 headache). This is NOT the same as *serious*, which is based on patient/event outcome or action criteria described above, and is usually associated with events that pose a threat to a patient's life or ability to function. A severe AE (Grade 3 or 4) does not necessarily need to be considered serious. For example, a white blood cell count of 1000/mm³ to less than 2000 is considered Grade 3 (severe) but may not be considered serious. Seriousness (not intensity) serves as a guide for defining regulatory reporting obligations.

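### Section 8.2 exempts non-serious anorexia and nausea/vomiting from adverse-event recording whatever their cause, so drug-related, mainly Grade 3, cases need not be recorded.

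*Combined protocol and SAP*

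**What the plan says.** Section 8.2 collects all adverse events of Grade 3 and above, whatever their relationship to treatment, apart from certain laboratory findings and a list of exceptions. On lower grades it says "Grade 1 and 2 events will not be collected". The exception list opens with "The following are frequent events in the chronic GVHD population and will not be recorded as adverse events", on the condition that the event is not serious. Its gastrointestinal item includes "anorexia, difficulty swallowing due to esophageal stricture or narrowing, nausea/vomiting, salivary gland changes, GVHD associated abdominal pain, bloating, diarrhea, weight loss".

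Elsewhere the protocol treats some of these symptoms as effects of the drug. Section 6.1 says "Due to the common side effect of nausea, it is recommended (but not required) that participants take Zofran". Section 6.6 says "Adverse drug reactions such as thrombocytopenia, diarrhea, fatigue, nausea, vomiting, and rash have been associated with Ixazomib treatment". Table 6-3 calls for action on study drug when a Grade 3 non-hematologic toxicity is judged drug-related.

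On seriousness, section 8.1 says "A severe AE (Grade 3 or 4) does not necessarily need to be considered serious". Section 8.2 already uses a causality test for another purpose: events later than 30 days after the last dose "will be recorded only if there is a reasonable possibility that the event was caused by a study procedure or Ixazomib".

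**The concern.** Because Grade 1 and 2 events are never collected, the exception list can only remove events of Grade 3 or higher. For anorexia and nausea/vomiting the only condition for removal is that the event is not serious. An investigator could judge a Grade 3 episode of vomiting to be caused by ixazomib and act on study drug under Table 6-3, yet have no duty to record an adverse event.

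The non-serious compilation sent to the DSMB (8.2) and the IND Annual Report (8.3) are built from collected events. Section 7.1.2 states that ixazomib has not been studied before in this setting, so the tolerability record would be incomplete for toxicities that the protocol itself expects.

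A secondary matter is consistency between sites. The words *GVHD associated* stand before abdominal pain, and the text does not say whether they carry on to bloating, diarrhea and weight loss.

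**Working it through.** **Step 1: does the text limit the exemption by cause?** The items of the exception list differ:

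| Item in 8.2 | Condition on cause |
|---|---|
| Ocular dryness | GVHD-related |
| Rash | GVHD rash |
| Respiratory symptoms | Tied to lung involvement by chronic GVHD |
| Abdominal pain | GVHD-associated |
| Bloating, diarrhea, weight loss | Unclear; the qualifier two words before abdominal pain may carry on |
| Anorexia | None |
| Nausea/vomiting | None |

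Where the list limits by cause, it says so. The lead-in explains why the list exists. It does not test the cause of an individual event.

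**Step 2: does anything restore drug-related cases?**
- The clause on worsening belongs to a separate item, abnormalities present at enrollment.
- Section 8.3 gives expedited reporting to serious events only; its annual report covers events that were collected.
- Section 8.5 asks for the relationship of non-serious events to study drug, but does not override the exceptions.
- The causality test in 8.2 applies only to late events.

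Nothing restores them.

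**Step 3: which grades are affected?** The general definitions in 8.1 make Grade 4 life-threatening, and a life-threatening event is serious. Those definitions formally apply to events outside CTCAE, and 8.1 allows a Grade 3 or 4 event to be non-serious. So the gap lies mainly, though not provably only, at Grade 3.

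**Step 4: scale, as an illustration.** The plan states no figure to reproduce. The inputs are the drug-related Grade 3+ rates for C16004 in Table 1-4 (N = 52) and the planned 50 patients (4.2).

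| Event | Rate | Patients of 52 | Per 50 = 50 × patients / 52 |
|---|---|---|---|
| Nausea | 8% | 4 (4/52 = 7.7%) | 3.8 |
| Decreased appetite | 8% | 4 (7.7%) | 3.8 |
| Vomiting | 6% | 3 (3/52 = 5.8%) | 2.9 |

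Patients with at least one of the three:
- Lower end, full overlap: 4/52 × 50 = 3.8, about 4.
- Upper end: section 1.6 reports one patient at 2.97 mg/m² with Grade 3 nausea, vomiting and diarrhea together. If this dose-limiting event is counted as drug-related, at least one patient has both nausea and vomiting. The maximum is then 4 + 4 + 3 − 1 = 10, and 10/52 × 50 = 9.6, about 10.
- If the similar description at 3.95 mg/m² is also one patient, the maximum is 9, and 9/52 × 50 = 8.7.

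**The case against.** The strongest reply is that limited collection is a deliberate choice. Symptoms of chronic GVHD are frequent and hard to interpret, serious cases still reach the database within 24 hours, the protocol has no safety objective, and section 7.1.1 plans no adverse-event analysis. This stands as a reason to rate the point modestly. It does not explain why drug-attributed events should be exempt when other items on the same list are limited to GVHD.

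A second reply is that many Grade 3 events will be serious, since the general grade definitions mention hospitalization. That narrows the gap but does not close it, because 8.1 keeps severity and seriousness apart.

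Some stronger readings are tempting but not supported:
- **That drug-related diarrhea is exempt too.** C16004's 17% would be 8.5 of 50 patients. But a leading qualifier before a run of parallel nouns most naturally governs them all, and on that reading drug-related diarrhea is recorded. Only the ambiguity can be claimed.
- **That the three rates can simply be added, giving 11 patients of 52.** The patient with combined nausea and vomiting in section 1.6 rules this out, on the assumption stated in the working.
- **That C16007 shows a rate near zero.** Its Grade 3+ row is headed with a threshold on patient numbers and omits a Grade 3 diarrhea that the text reports. Absence from that row is not a zero count.

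**Conclusion.** The point holds on the wording of 8.2. Non-serious anorexia and nausea/vomiting of Grade 3 or higher are exempt from recording even when judged related to ixazomib, and so drop out of the DSMB compilation and the IND Annual Report. The reach of the GVHD qualifier over bloating, diarrhea and weight loss is a lesser ambiguity on which sites could differ.

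On the illustration, about 4 to 10 of 50 patients would have at least one such drug-related event. This is not a bound for the trial:
- The non-serious share is not given, so the number unrecorded runs from none upward.
- C16004 included doses above the equivalent of 4 mg (about 2.23 mg/m²), with expansion cohorts at 2.97 mg/m², and ondansetron is recommended here. Both point to lower rates.
- C16004 patients had received a median of 2 cycles, against up to 6 or 12 here, which points the other way.

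A reader might infer that safety oversight as a whole is compromised. The documents do not support that: serious-event reporting, the mortality stopping rule, the primary endpoint and power are unaffected. This is a cheap improvement to the safety record, and it rests on the text rather than on the numbers.

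**What to change.** Add one sentence to section 8.2, for example:

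*The gastrointestinal exceptions apply only to events attributed to chronic GVHD or to another cause other than study drug; Grade 3 or higher anorexia, nausea, vomiting, abdominal pain, bloating, diarrhea or weight loss with a reasonable possibility of being caused by ixazomib is recorded even if not serious.*

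This settles both the missing condition and the reach of the qualifier, using a test that 8.2 already contains and 8.1 defines. Events attributed to GVHD stay exempt, so the purpose of the list is kept.

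The cost is a small number of extra adverse-event entries. For nausea, vomiting and anorexia, on the illustration, they would come from none to about 10 patients. Section 8.5 limits the entries further by asking that symptoms of one underlying pathology be noted together where possible. No new assessments are needed, because relationship to study drug is already judged under 8.5 and Table 6-3.
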